7.7. Safety Analyses

7.7.1. Study Intervention Exposure

The number of injections will be summarized using frequency and percentage by the treatment group, and by single foot treated or both feet treated using Safety Population. Summary using ITT Population, mITT population and FAS Population will be provided, only if these populations are not identical to the Safety Population.

A separate listing of study intervention exposure for each treatment group will be provided using ITT Population, mITT population and FAS Population, only if these populations are not identical to the Safety Population.

7.7.2. Safety by Incidence of TEAEs, AESIs, SAEs

The safety of treatment groups is assessed by incidence, severity and duration of treatment emergent adverse events (TEAEs), adverse events of special interest (AESIs), AEs resulting in study discontinuation and serious adverse events (SAEs).

The risk difference and associated 95% CI using the exact method will be presented for incidence of TEAEs, TEAEs resulting in drug discontinuation, and TEAEs leading to study discontinuation across treatments.

All AE summary tables will include only TEAEs, unless otherwise specified.

TEAEs will be summarized by SOC and PT. A participant will only be counted once per SOC and PT.

For TEAEs by severity grade (Grade 1, Grade 2, Grade 3, Grade 4 and Grade 5), if a participant has multiple events occurring in the same SOC or same PT, then the event with the highest grade will be counted.

For TEAEs by relationship to study intervention, if a participant has multiple events occurring in the same SOC or same PT, the event with the highest association (ie, related) to study intervention will be summarized.

AEs will be presented in decreasing order of the incidence at SOC level and within each SOC, in decreasing order of the incidence at the PT level.

An overall summary of TEAEs and TEAEs related to study intervention will be presented and will include:

- Total number of TEAEs reported
- Total number of TEAEs reported by severity
- Participants with any TEAE
- Participants with any serious TEAE
- Participants with any TEAE of special interest
- Participants with any Grade 3+ TEAE
- Participants with no Grade 3+ TEAEs, but at least one Grade 2 TEAE
- Participants with no Grade 3+/Grade 2 TEAEs, but at least one Grade 1 TEAE
- Participants with any TEAEs leading to drug interruption/discontinuation
- Participants with any TEAEs leading to withdrawal from study
- Participants with any TEAEs resulting in death

The following summary tables will be presented by SOC and PT:

- All TEAEs
- TEAEs by severity
- TEAEs by special interest
- Treatment related TEAEs
- Treatment related TEAEs by severity
- Serious TEAEs
- Serious treatment related TEAEs
- TEAEs resulting in death
- Study intervention related TEAEs resulting in death
- Duration of treatment related TEAEs (Duration of treatment related TEAEs (<14 days, 14 – 21 days and >21 days) (Refer to [Table 25](#) for computation of duration of AEs.)

The most common serious and non-serious TEAEs by order of frequency (most frequent, 2nd most frequent, 3rd most frequent and so on) will be summarized by PT. The most common serious and non-serious AEs are those with any PT that at least 5% of the Participants reported at least once.

The following listings will be presented by participant:

- All AEs

- Serious AEs
- AEs of special interest
- AEs resulting in drug interruption/discontinuation
- AEs resulting in study withdrawal
- AEs resulting in death

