EN3835 was well tolerated. During the Initial Treatment and Retreatment Periods, there were no serious adverse events (SAEs), and no TEAEs leading to death, EN3835 discontinuation, or study withdrawal. Common TEAEs included: injection site pain, injection site swelling, and injection site bruising, with the majority resolving within 21 days. On Day 57 of the Retreatment Period, all participants tested (10/10; 100%) had detectable neutralizing AUX-I antibodies and almost all participants (8/10; 80%) tested had detectable neutralizing AUX-II antibodies. There were no clinically relevant findings in participants with detectable anti-AUX-I, anti-AUX-II, or neutralizing AUX-I and AUX-II antibodies.

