
 To assess the safety and tolerability of EN3835 in participants with plantar fibromatosis. 	
 Safety of EN3835 as assessed by incidence, severity and duration of treatment-emergent adverse events (TEAEs), adverse events of special interest (AESIs), and serious adverse events (SAEs). The change from baseline in vital signs and clinical laboratory values at each visit where these parameters are measured.

 To assess the immunogenicity of EN3835 in participants with plantar fibromatosis. 	
 Presence of anti-AUX-I and anti-AUX-II antibody titer levels in EN3835 treated-participants at Day 1 and Day 57. Presence of neutralizing antibodies to AUX-I and AUX-II in EN3835 treated-participants at Day 1 and Day 57.
Exploratory	

 To assess the overall improvement in the FFI composite score with EN3835 vs placebo. 	
 The difference between EN3835 and placebo in the mean change from Baseline (Day 1) to Day 57 on the FFI composite score, with the score of each of the 21 items ranging from 0 to 4, with 4 indicating higher severity. The mean change from Baseline (Day 1) to Days 15, 29, 43, and 57 on the FFI composite score with EN3835 vs placebo.

 To assess the overall improvement in severity of plantar fibromatosis on the Patient Global Impression of Severity (PGIS) PF Overall scale. 	
 The difference between EN3835 and placebo at Day 57 on the PGIS PF Overall score. The difference between EN3835 and placebo Days 15, 29, 43, and 57 on the PGIS PF Overall score with EN3835 vs placebo.

 To assess the overall improvement in the severity of foot pain with EN3835 vs placebo in the PGIS foot pain subscale. 	
 The difference between EN3835 and placebo at Day 57 on the foot pain subscale of the PGIS. The difference between EN3835 and placebo at Days 15, 29, 43, and 57 on the PGIS foot pain subscale, ranging from 0 ("None") to 4 ("Severe") with EN3835 vs placebo.

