
 To assess the safety and tolerability of EN3835 in participants with plantar fibromatosis. To assess the immunogenicity of EN3835 in participants with plantar fibromatosis. 	
 Safety of EN3835 as assessed by incidence, severity, and duration of treatment-emergent adverse events (TEAEs), adverse events of special interest (AESIs), and serious adverse events (SAEs). The change from baseline in vital signs and clinical laboratory values at each visit where these parameters are measured. Presence of anti-AUX-I and anti-AUX-II antibody titer levels in EN3835 treated-participants at Day 1 and Day 57. Presence of neutralizing antibodies to AUX-I and AUX-II in EN3835 treated-participants at Day 1 and Day 57.

Table 1: Objectives and Endpoints (Continued)

Objective	Endpoint
Exploratory	

 To assess the overall improvement in the FFI total score with EN3835 vs placebo 	
 The difference between EN3835 and placebo in the mean change from Baseline (Day 1) to Day 57 on the FFI total score of 21 items with the score of each item ranging from 0 to 4, with 4 indicating higher severity. The mean change from Baseline (Day 1) to Days 15, 29, 43, and 57 on the FFI total score with EN3835 vs placebo.

 To assess the overall improvement in severity of plantar fibromatosis on the Patient Global Impression of Severity (PGIS) PF Overall scale. 	
 The difference between EN3835 and placebo at Day 57 on the PGIS PF Overall score. The difference between EN3835 and placebo Days 15, 29, 43, and 57 on the PGIS PF Overall score with EN3835 vs placebo.

 To assess the overall improvement in the severity of foot pain with EN3835 vs placebo in the PGIS foot pain subscale 	
 The difference between EN3835 and placebo at Day 57 on the foot pain subscale of the PGIS. The difference between EN3835 and placebo at Days 15, 29, 43, and 57 on the PGIS foot pain subscale, ranging from 0 (“None”) to 4 (“Severe”) with EN3835 vs placebo.

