4.9.1.3. Relationship to Study Intervention

The causal relationship with study intervention will be classified by the investigator and will be reported as follows:

- Not related
- Unlikely related
- Possibly related
- Probably related

Related adverse events are TEAEs with the relationship described by the investigator as “probably related” or “possibly related”. “not related” or “unlikely related” causality assessments are considered as not related.

Any missing relationship of an AE to study intervention will be considered as related to study intervention for the analyses, following worst case principle.

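### Duration is part of the stated safety endpoint for all TEAEs, AESIs and SAEs, but the only by-arm duration summary that SAP 7.7.2 lists is limited to TEAEs rated treatment-related

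*SAP*

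**What the plan says.** The endpoint carries no relatedness qualifier wherever it is stated.

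- Protocol Section 4: "incidence, severity and duration of treatment-emergent adverse events (TEAEs), adverse events of special interest (AESIs), and serious adverse events (SAEs".
- SAP Section 2, Table 1: "incidence, severity, and duration of treatment-emergent adverse events (TEAEs), adverse events of special interest (AESIs), and serious adverse events (SAEs".
- SAP 7.7.2, opening sentence: "incidence, severity and duration of treatment emergent adverse events (TEAEs), adverse events of special interest (AESIs", followed by AEs leading to study discontinuation and SAEs.

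SAP 7.7.2 then lists ten tables by SOC and PT. The only one on duration is "Duration of treatment related TEAEs (Duration of treatment related TEAEs", banded at <14, 14-21 and >21 days.

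The filter is defined in SAP 4.9.1.3. "Related adverse events are TEAEs with the relationship described by the investigator as" probably or possibly related. Ratings left blank are added: "Any missing relationship of an AE to study intervention will be considered as related to study intervention for the analyses".

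SAP 6.2, Table 25, derives duration for any AE (end date minus start date, plus one day), whether or not it is related.

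**The concern.** An endpoint with three components should have a summary by treatment group for each, on the events the endpoint names. Here one component is summarised on a subset, and the SAP does not say why.

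Two things follow. First, a reader of the study report could not see from the tables how long TEAEs in general lasted in each arm. The programme's background statements on duration, such as those in Protocol 3.1 and 5.2 that most AEs resolved within 21 days, are not limited to related events, so the planned table cannot be set beside them directly.

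Second, membership of the subset is decided after randomisation by an investigator who also examines the treated foot. Protocol 3.2.1 reports from the proof-of-concept study: "Common TEAEs included: injection site pain, injection site swelling, and injection site bruising". Swelling and bruising can be seen. If such signs led an investigator to guess the arm, similar events could be attributed differently in the two groups, and the related-only table would reflect attribution as well as duration.

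**Working it through.** **Step 1. Compare the endpoint with the listed summaries.** No figure in the plan bears on this point, so the check is of text against text.

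| Component | Table for all TEAEs in SAP 7.7.2 | Table for related TEAEs in SAP 7.7.2 |
|---|---|---|
| Incidence | yes | yes |
| Severity | yes | yes |
| Duration | none listed | yes |

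AESIs and serious TEAEs have their own incidence tables but no duration table. Those rated related would fall within the related-only duration table; those rated not or unlikely related would not. The overall TEAE summary in the same section has no duration line.

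**Step 2. Look for the missing summary elsewhere.**

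- Protocol 10.3.2.1 (Adverse Events) covers incidence and severity and names no duration analysis.
- SAP Section 8, Table 28 (changes from protocol) has one entry, on prior medications. It does not mention limiting duration to related events.
- SAP 7.7.2 plans participant listings of all AEs, serious AEs and AESIs, and SAP 6.1 promises listings of derived variables. Individual durations should therefore be available, but a listing is not a summary by arm.

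**Step 3. What the filter could do to the counts.** Neither document gives attribution rates by arm, so every rate here is an assumption. Take 86 treated participants per arm (the planned size), at most one TEAE lasting >21 days per participant, and the same true risk *r* in both arms. Let *a* and *p* be the probabilities that such an event is called related on EN3835 and on placebo.

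- All-TEAE table: 86 × *r* expected in each arm.
- Related-only table: 86 × *r* × *a* against 86 × *r* × *p*.
- Difference produced by the filter alone: *r* × (*a* − *p*).

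With *r* = 0.20, *a* = 0.60, *p* = 0.30:

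- all TEAEs: 86 × 0.20 = 17.2 against 17.2;
- related only: 17.2 × 0.60 = 10.3 against 17.2 × 0.30 = 5.2;
- difference: 0.20 × 0.30 = 6 percentage points, with no true difference.

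Across *r* = 0.10 to 0.30, the smallest assumed gap (40% against 20%) at the lowest risk gives 0.10 × 0.20 = 2 points. The largest (80% against 20%) at the highest risk gives 0.30 × 0.60 = 18 points. With equal attribution (50% in both arms) the difference is 0, although half of the long events still drop out of each arm.

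This shows the mechanism and its direction. It does not estimate what will happen in this trial.

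**The case against.** The strongest case against is that this is a gap in display with little resting on it.

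- **Reporting is not absent.** Duration is derived for every AE and participant listings are planned, so a reader might wrongly infer that the duration endpoint, or the duration of AESIs and SAEs, goes unreported. The documents do not support that. What is missing is a by-arm summary. This part of the objection stands.
- **Differential attribution is not shown.** The trial is double-blind, placebo is a volume-matched intralesional injection, and relatedness is rated to study intervention, which includes placebo. A needle reaction on placebo can be rated related, and blank ratings count as related in both arms. The report of common local reactions comes from an open-label study without a placebo group. A reader might infer that the duration table is biased; the documents support only a risk. This stands too.
- **The illustration concerns counts, not durations.** If attribution does not depend on how long an event lasts, the expected split of the retained events across the three bands is unchanged; only the number retained shifts. This is correct and limits what Step 3 shows.
- **No inference is attached.** The risk differences with 95% CIs in SAP 7.7.2 are for incidence of TEAEs and of TEAEs leading to drug or study discontinuation, none filtered by relatedness. This stands and keeps the severity low.
- **AESIs and SAEs may be few.** The proof-of-concept study had no SAEs. Separate banded tables could be nearly empty and a listing may serve as well. The fix allows for this.
- **The table shells were not available.** They are in SAP Module 2, which is not among the documents, so an unlisted all-TEAE duration table cannot be ruled out. If one exists, SAP 7.7.2 should list it.

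None of these points explains why duration alone lacks an all-TEAE summary when incidence and severity have both versions.

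**Conclusion.** The mismatch holds on the text. Duration is the one component of the stated safety endpoint with no listed by-arm summary for all TEAEs, and events rated not or unlikely related reach the reader only through listings. That conclusion assumes that the tables listed in SAP 7.7.2 are the complete set.

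The further point, that the related-only table could differ by arm for reasons other than duration, is a design risk that depends on attribution differing between arms. Its size cannot be computed from the documents; the 2 to 18 points above follow from assumed rates, and equal attribution gives zero.

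Severity is low. The table is descriptive, no efficacy result and no planned safety interval depends on it, and incidence and severity are summarised for all TEAEs.

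**What to change.** In SAP 7.7.2:

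1. Add a descriptive table of duration (<14, 14-21, >21 days) for all TEAEs by SOC, PT and treatment group.
2. Show AESIs and serious TEAEs as rows of that table or, if there are few, give the derived duration in the listings already planned for them.
3. Keep the treatment-related duration table as supportive.

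The cost is one SAP line and one or two more descriptive tables. The dates are already collected and the derivation in Table 25 already applies to every AE.

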7.7.3. Vital Signs

Vital signs (systolic and diastolic blood pressure, pulse rate, respiratory rate, and body temperature) will be summarized by treatment group and overall (if applicable) using descriptive statistics for observed and change from Baseline values for all post-baseline assessment visits.

The PCI vital signs values will be summarized by treatment group and overall using frequency and percentages separately for each treatment. Refer to [Table 23](#) for PCI criteria.

A separate listing will be presented for vital sign results by participant.

7.7.4. Clinical Laboratory

Hematology and chemistry results will be summarized by treatment group and overall (if applicable) using descriptive statistics for observed and change from Baseline values at each visit.

The PCI laboratory values will be summarized by treatment group and overall (if applicable) using frequency and percentages. The participants with treatment-emergent PCI values will be summarized. The pre-treatment PCI values can be found in individual listings. Refer to [Table 22](#) for PCI criteria.

Additionally, shift tables will be produced by treatment group and overall. The shift tables will be based on the classification of laboratory results (ie, low, normal, high) at Day 57/EOS compared to the classification of baseline results.

A listing for hematology, chemistry and urinalysis results will be presented for all laboratory parameters by participant. Serum and urine pregnancy test and urine drug screen results will be listed separately by participant.

7.7.5. Physical Examination

Physical examination results (by body system) at Baseline, at Day 29, and Day 57/EOS will be presented by treatment group and overall (if applicable) using frequency and percentages separately by treatment.

A listing will be presented for physical examination results (by body system) for each visit as per the SoA ([Table 2](#)) by participant.

7.7.6. Foot Examination

Foot examination results will be presented by visit, treatment group and overall (if applicable) using frequency and percentages separately by treatment.

A listing will be presented for foot examination results for each visit as per the SoA ([Table 2](#)) by participant.

7.7.7. Immunogenicity

7.7.7.1. Presence of anti-AUX-I and anti-AUX-II antibody titer levels

The following will be summarized: the number of participants with an immunogenicity sample collected, the percentage of participants with positive and negative anti-AUX-I and anti-AUX-II antibodies, the titer level of the positive samples at Screening and Day57/EOS.

The titer levels will be logarithmically transformed prior to being summarized. Samples from Screening and Day 57/EOS will be analyzed for anti-AUX-I and anti-AUX-II antibodies.

7.7.7.2. Presence neutralizing antibodies to AUX-I and AUX-II

A subset of positive samples of AUX-I or AUX-II will be analyzed for neutralizing antibodies. Neutralizing antibody results will be summarized as percentage of positive/negative results by visit and treatment group if applicable.

A listing of immunogenicity results by participant will be provided.

8. CHANGE FROM PROTOCOL

This SAP is based on Clinical Study Protocol Amendment 04, dated 10 June 2022.

Table 28: Changes from Protocol

Text in Protocol	Text in SAP	Justification
Section 7.7.1: The start and stop date, dose, unit, frequency, route of administration, and indication for all prior medications (taken within the 30 days prior to the Screening Visit) and nondrug therapies (eg, blood transfusions, oxygen supplementation, physical therapy, etc) received will be recorded.	Any medication/procedure taken/done prior to first injection (Day 1) will be reported as prior medication/procedure.	It was observed in the proof-of-concept study EN3835-105 that there were medications which remain unclassified because the medications were taken > 30 days prior to screening visit. This change is intended to ensure that all prior medications taken, even if > 30 days are classified.

10. APPENDIX

All the SAS codes will be provided in Module 2.

11. TABLES, LISTINGS, AND GRAPH SHELLS

The layouts of the summary tables, participant listings, and graphs are presented in [SAP Module 2](#). These layouts incorporate all the appropriate table titles, table numbers, and footnotes.
